## **1.0 BACKGROUND AND RATIONALE**

### **1.1 Study Synopsis**

The purpose of the study is to assess the utility of combined, simultaneous positron emission tomography (PET) and magnetic resonance imaging (MRI), collectively called PET-MR, in assessing response to neoadjuvant radiation therapy in the treatment of high grade sarcomas. Adult patients with potentially curable high grade sarcomas that are being treated at UNC with neoadjuvant radiation therapy followed by potentially curative surgical resection will be recruited through the Department of Surgery. Patients who are being treated for potentially curable high grade sarcomas with neoadjuvant radiation therapy followed by surgical resection will undergo pre-treatment, mid-treatment, and post-treatment PET/MR and the response to treatment will be assessed at mid-treatment and post-treatment time points by evaluating change in tumor size from MRI and 18F-fluorodeoxyglucose (18F-FDG) avidity from PET. Patients will then undergo curative intent resection. Their pathology will be reviewed for treatment effect as assessed by percent necrosis, size, and resection margins. Patients will be followed and assessed for recurrence.

This study is designed to provide preliminary information on the progression of tumor size and FDG avidity during and after treatment in 30 patients diagnosed with potentially curable high-grade sarcomas. The primary objective is to evaluate the capabilities of PET and MRI, individually and combined, in early prediction of patients who will and will not respond to neoadjuvant radiation therapy. A secondary objective will be to quantify the progression of PET- and MRI-based metrics at pre-, mid-, and post-treatment time points.

Information from this study may be used to estimate effect size for power calculation and sample size considerations for possible future studies in the use of combined PET-MR to predict, at a mid-treatment time point, which sarcoma patients will respond to, and therefore continue with, neoadjuvant radiation therapy, and which patients will not respond and should be spared additional time and radiation dose before proceeding to surgery.

### **1.2 Background**

The only curative treatment for non-metastatic sarcomas is complete surgical resection. Nonetheless, most patients who undergo curative intent surgery will have positive gross or microscopic margins. Of those who are treated with complete resections, a large proportion will recur locally. Radiation has been shown to improve the rate of complete resection, and improve local control rates. Neoadjuvant radiation has even been shown to improve 3 year overall survival in high grade extremity sarcomas. The utility of radiation in the treatment of sarcomas has been shown in multiple studies. Still, utilization of adjuvant and neoadjuvant radiation in the United States remains low. This is partially related to the large discrepancy within subtypes of sarcomas and varied response to radiation among different grades of sarcoma within the same subtype. The underutilization of neoadjuvant radiation

is also partly in due to some controversy about which patients should undergo neoadjuvant radiation as opposed to adjuvant radiation versus no radiation at all.

PET/CT and MRI are two modalities that are utilized in the diagnosis, treatment, and follow up of extremity soft tissue and retroperitoneal sarcomas. PET activity has been shown to correspond with treatment response in many tumor types. MR has a specific advantage in imaging of soft tissues which is especially important in extremity and retroperitoneal sarcomas. An integrated PET/MR system has the potential benefit of reducing patient time, and expenditures, as well as avoiding the ionizing radiation associated with CT. Further the integrated system has the potential for greater anatomical detail in the context of FDG activity. The University of North Carolina leads in the utilization of neoadjuvant radiation for sarcoma and has one of the few combined PET-MR imaging systems in the US.

There exists a need to identify those patients with high grade sarcomas who will benefit from neoadjuvant radiation therapy. This will enable us to focus our resources on delivering effective radiation therapy to those patients who will benefit from them and minimize the associated risks and consequences of radiation in those patients who will not benefit from them and allow those patients to move quickly to curative intent surgery.

### **1.3 Purpose and Rationale**

This is a prospective study of the use of combined PET-MR [1-7] for assessment of response to neoadjuvant radiation therapy in high-grade sarcomas. There are no prior studies evaluating combined, simultaneous PET-MR for this purpose, although studies indicate that PET, at a mid-treatment time point, is predictive of response to neoadjuvant chemotherapy in sarcomas [8] and that PET and MRI, acquired separately, are correlated with response to neoadjuvant chemotherapy at a post-treatment time point [9]. These studies suggest our guiding hypothesis: that simultaneous PET and MRI, acquired at a mid-treatment time point, provide image-based quantitative measures that are associated with and predict response to neoadjuvant radiation therapy in high-grade sarcomas. If so, in the future, application of PET-MRI at mid-treatment may be used to determine the course of treatment for patients at this stage, whether to continue neoadjuvant therapy, or to spare time, expense, and radiation dose for nonresponders.

We propose that a PET/MR study at the midpoint of radiation treatment will accurately predict which patients will respond to neoadjuvant radiation therapy. We will enroll patients with high-grade sarcomas as identified by preoperative biopsy that will be treated with neoadjuvant radiation into the study. The standard of care for these patients is to receive MRI scans at pre-treatment and post-treatment time points. Patients in our study will receive their standard pre- and post-treatment imaging in the form of PET/MR, with PET conducted simultaneously with MRI, and within the context of the study they will also receive one additional PET/MR at the end of the second week of therapy. These patients will then receive curative intent surgery and be followed

in the usual fashion and assessed for local and/or distant recurrent disease. The pathology will be assessed for completeness of resection and percent of necrosis. On the basis of pathology, patients will be classified as responsive or non-responsive to therapy. Quantitative measures from PET and MRI will be computed: the change in PET tumor-mean standardized uptake value (SUV) and tumor size as assessed by MRI, from pre- to post-treatment, and from pre- to mid-treatment. The image-based quantitative measures will be correlated with the pathology outcomes to evaluate predictability of the image measures for treatment response. Patients will be followed with the intent of further correlating image measures with clinical outcomes.

## **2.0 STUDY OBJECTIVES/AIMS AND ENDPOINTS**

### **2.1 Primary objectives**

- 2.1.1** Determine whether there is a significant difference between response groups in PET mean SUV fractional change (baseline to mid-treatment).

### **2.2 Secondary objectives**

- 2.2.1** Determine whether there is a significant difference between response groups in MRI tumor size fractional change (baseline to mid-treatment).
- 2.2.2** Determine whether there is a significant difference between response groups in PET mean SUV fractional change (baseline to post-treatment).
- 2.2.3** Determine whether there is a significant difference between response groups in MRI tumor size fractional change (baseline to post-treatment).
- 2.2.4** Assess the correlation in PET mean SUV change and MRI tumor size change from baseline to mid-treatment, in addition to baseline to post-treatment.

### **2.3 Exploratory Objectives**

- 2.3.1** To assess the utility of combined, simultaneous positron emission tomography (PET mean SUV) and magnetic resonance imaging (MRI tumor size), in early prediction of response to neoadjuvant radiation therapy in the treatment of high-grade sarcomas at mid-treatment and post-treatment.
- 2.3.2** Examine the utility of using maximal SUV in place of mean SUV in prediction of response

### **3.0 PATIENT ELIGIBILITY**

#### **3.1 Inclusion Criteria**

Subject must meet all of the inclusion criteria to participate in this study:

- 3.1.1** Age  $\geq 18$  years of age (no upper age limit)
- 3.1.2** Signed, IRB-approved written informed consent
- 3.1.3** Must have a biopsy-proven high-grade retroperitoneal or soft tissue extremity sarcoma confirmed by independent evaluation of a UNC sarcoma specialized pathologist.
- 3.1.4** Must have surgically curable disease as evaluated by initial imaging by our UNC surgeons.
- 3.1.5** Must be in acceptable health to undergo radiation therapy and curative intent surgery as assessed by UNC surgeons and radiation oncologist.
- 3.1.6** Must be able to understand and comply with study procedures for the entire length of the study.
- 3.1.7** Must receive their neoadjuvant radiation therapy and curative intent surgery at UNC Hospitals – Chapel Hill location.
- 3.1.8** Women of childbearing potential must have a negative serum or urine pregnancy test performed within 7 days prior to first PET/MRI

#### **3.2 Exclusion Criteria**

[figure not shown]
Any subject meeting any of the following exclusion criteria at baseline will be ineligible for study participation:

- 3.2.1** Inability to tolerate MRI (e.g., inability to lie flat for >1 hour)
- 3.2.2** Presence of pacemaker, intracranial aneurysm clip, bladder stimulator, cochlear implant or metal near eyes or near pelvis that would create excessive imaging artifact
- 3.2.3** Poorly controlled diabetes mellitus
- 3.2.4** Creatinine > 1.4 mg/dL **OR** GFR < 30mL/min
- 3.2.5** Body Mass Index (BMI) > 35
- 3.2.6** Active vaginal bleeding requiring packing and emergent radiation therapy
- 3.2.7** Pregnancy or lactating female
- 3.2.8** History of a prior malignancy within past 5 years are excluded unless they have been disease free for 3 or more years
- 3.2.9** Substance abuse, medical, psychological, or social conditions that may interfere with the patient's participation in the study

- 3.2.10 Evidence of distant disease on physical exam or initial imaging
- 3.2.11 Medical conditions precluding radiation therapy or curative intent surgery
- 3.2.12 Previous radiation exposure precluding radiation therapy
- 3.2.13 Incarcerated or otherwise institutionalized at time of enrollment

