Patients will then be scheduled for a pre-treatment PET/MR and proceed to neoadjuvant radiation therapy per the direction of the radiation oncologist. At the end of the second week of radiation therapy the patient will undergo a mid-treatment PET/MR. The patient will complete their radiation therapy. Four weeks after radiation therapy the patient will undergo a post-treatment PET/MR, and proceed for curative intent surgery at 6-8 weeks post radiation if they are still surgical candidates.

For all PET scans, patients will be instructed to fast, and blood glucose levels will be measured prior to imaging. Patients will be injected with 12 mCi 18-FDG, and then imaged starting 60 minutes post-injection for ten minutes each at one or two bed positions focused on the primary tumor site. MRI sequences to be run will include conventional anatomic T1- and T2-weighted sequences, high-resolution T1 pre- and post-contrast sequences, and the Dixon PET-MR attenuation-correction sequence.

The PET/MRs at each time point will be evaluated by UNC radiologists as to the size of the lesion, the FDG activity as measured by tumor-maximum and tumor-mean standard uptake values (SUVs), the presence or absence of invasion to adjacent organs, and the presence or absence of metastatic or multifocal disease. PET images will be evaluated with aligned anatomical MRI for guidance as well as determination of the tumor margins for computation of tumor-mean SUV.

The UNC surgeons will record the resectability of the tumor, and the gross appearance of the resection (R0-grossly negative, R2-grossly positive), as well as any evidence of metastatic disease, presence or absence of invasion to surrounding organs, or multifocal disease. The PET/MRs will be evaluated by UNC radiologists as to the size of the lesion, the FDG activity as measured by SUVmax and SUVmean,

the presence or absence of invasion to adjacent organs, and the presence or absence of metastatic or multifocal disease. The pathological specimens will be evaluated by a UNC pathologist specialized in sarcoma as to the degree of necrosis (none, <10%, 10-50%, 51-90%, >90%, 100%), status of margins (R0-negative margins, R1-microscopically negative margins, R2 – grossly positive margins), the presence and absence and number of affected lymph node involvement if applicable, and presence or absence of invasion to adjacent organs. Again, all data will be stored on a secured, password protected server.

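### The metal-artefact exclusion in 3.2.2 is tied to the eyes and pelvis, not to the imaged tumour site, so a patient with artefact-producing metal beside many limb tumours stays eligible

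*Combined protocol and SAP*

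**What the plan says.** Criterion 3.2.2 (section 3.2, Exclusion Criteria) lists several implanted devices and then "metal near eyes or near pelvis that would create excessive imaging artifact". The stated reason for the metal clause is image quality, but the sites it names are fixed.

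Section 3.1 (criterion 3.1.3) admits a "high-grade retroperitoneal or soft tissue extremity sarcoma". Section 7.1 says that PET is acquired at "one or two bed positions focused on the primary tumor site".

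Section 7.1 also makes PET quantification depend on MRI in two ways. The sequences include "the Dixon PET-MR attenuation-correction sequence", and PET is read with "aligned anatomical MRI for guidance as well as determination of the tumor margins for computation of tumor-mean SUV". The primary objective (2.1.1) is the fractional change in mean SUV from baseline to mid-treatment, compared between response groups. Secondary objectives 2.2.1 and 2.2.3 use MRI tumour size.

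**The concern.** An exclusion meant to keep artefact out of the images should follow the part of the body that is imaged. Here that is the tumour site, which varies from patient to patient, while the criterion names two regions that do not vary. For a tumour in the forearm, calf or distal thigh, neither region is near the tumour, so metal beside it meets no exclusion.

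What is at stake is the validity of individual measurements. Artefact at the tumour can disturb the attenuation map, and so the SUV scale. It can also disturb the margin within which SUV is averaged, and the size measurement itself. The primary and two of the secondary comparisons could therefore be affected in the same patient. With 30 patients, even one or two uninformative values have a visible, though modest, effect on power.

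**Working it through.** **1. Does another rule close the gap?**

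| Place | What it covers | Catches metal at a limb tumour? |
|---|---|---|
| 3.2.2 | Named devices; metal near eyes or pelvis | Only if the tumour is near the pelvis |
| 3.2.9 | Conditions that interfere with participation | Not by its wording; image quality is not mentioned |
| 4.5 | Withdrawal for illness, adverse events, patient choice, changed condition | No; metal present at entry is not a change |
| 4.7 | Claustrophobia, need for lorazepam | No |
| 7.3 | Analysis plan | No image-quality check, no rule for an unreadable scan |

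Section 8.3 has the study coordinator verify the criteria before registration, so the written wording is what is applied.

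**2. How far could artefact affect the primary measure?** Let the true fractional change be f = (S_mid − S_pre)/S_pre. If artefact multiplies SUV by b1 at baseline and b2 at mid-treatment, the measured change f′ satisfies 1 + f′ = (b2/b1)(1 + f). With b1 = b2 the bias cancels. If the artefact or the drawn margin differs between scans, it does not. An additive bias does not cancel in general either. The documents support saying that values can be distorted, not that they will be.

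**3. The plan's own power.** Inputs from section 7.2: N = 30, p = P(X>Y) = 0.82, alpha 0.05, stated power about 90%. Both groups are written with the same n, so the split is taken as 15:15 (c = 0.5). Noether's formula, which the plan cites, is

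power = Φ(√(12c(1−c)N) × |p − 0.5| − z).

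√(12 × 0.25 × 30) × 0.32 = 9.487 × 0.32 = 3.036.

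- One-sided: Φ(3.036 − 1.645) = 91.8%.
- Two-sided: Φ(3.036 − 1.960) = 85.9%.

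The plan does not state sidedness for this test. Simulating the two-sided rank-sum test under a normal shift with P(X>Y) = 0.82 gives about 91%, in line with the stated figure. That is the baseline below.

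**4. Illustration of size.** The documents give no rate of metal near the tumour, so 1 or 2 affected patients of 30, chosen at random, is an assumption. The shift is √2 × Φ⁻¹(0.82) ≈ 1.29 standard deviations. Pure noise means that the value is replaced by a draw centred on the pooled mean, with no relation to response.

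| Affected patients' values (15:15, two-sided) | 0 affected | 1 affected | 2 affected |
|---|---|---|---|
| Pure noise, SD 1.2 | 90.8% | 88.6% | 84.8% |
| Signal kept, variance doubled | 90.9% | 90.2% | 89.2% |
| Patient dropped | 91.0% | 89.4% | 89.3% |

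Losses in points:
- Pure noise: 90.8 − 88.6 = 2.2 and 90.8 − 84.8 = 6.0.
- Doubled variance: 90.9 − 90.2 = 0.7 and 90.9 − 89.2 = 1.7.
- Dropped: 91.0 − 89.4 = 1.6 and 91.0 − 89.3 = 1.7.

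The first row depends on how wide the noise is: with SD 2 instead of 1.2, power is about 87% and 83%. Repeat runs agree within about a point, except that one run for a single dropped patient showed almost no loss. That is why the last two rows are summarised as a loss of about 0 to 2 points.

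**The case against.** The best defence is that the criterion covers more than it seems to. The retroperitoneum and the proximal thigh adjoin the pelvis, so the pelvic wording does protect the field for some tumours. That stands, and it limits the gap to other limb sites and the upper retroperitoneum. It would be wrong to say that the rule ignores the tumour field altogether.

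The primary measure is also a within-patient change with the same imaging at each visit, so fixed metal may bias both scans alike and partly cancel. That stands too. It makes pure noise the pessimistic end of the range rather than the expected case.

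Investigators may also screen out such patients informally. They may, but no written rule asks them to.

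A reader might draw three stronger conclusions that the documents do not support:

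- **Usable patients with pelvic metal are turned away.** The clause excludes only metal that would cause excessive artefact. Pelvic metal well outside the imaged field of a distal limb tumour would not naturally meet that condition.
- **The wording was carried over from a pelvic-cancer protocol.** The neighbouring criterion 3.2.6, "Active vaginal bleeding requiring packing and emergent radiation therapy", may prompt the thought, but nothing in the documents states the origin of either line. The gap does not depend on it.
- **The trial is left badly underpowered by this.** That needs a high rate of such metal or a very uneven responder split. The documents give neither, and an uneven split would be a separate sample-size matter.

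**Conclusion.** The mismatch is real and minor. The artefact clause does not follow the imaged site, and no other provision excludes or handles metal beside a mit- or distal-limb or upper retroperitoneal tumour. The mean SUV and MRI size changes of such a patient can be affected.

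The likely cost is small. With 1 or 2 of 30 patients affected, power stays within about 2 points of baseline if they are dropped or only noisier, and falls to about 89% or 85% if all signal is lost. These figures rest on an assumed number of affected patients, an equal split, a normal shift and a two-sided test. The route from artefact to SUV is inferred from the imaging methods in section 7.1; the documents do not quantify it.

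**What to change.** In 3.2.2, replace *near pelvis* with *in or near the tumour imaging field*, keeping the artefact condition and leaving the eye and device exclusions unchanged. Pelvic metal close to a lower retroperitoneal or proximal thigh tumour remains excluded under the new wording. Before the pelvic wording is removed, the sponsor should confirm that it serves image quality only, because 3.2.2 lists devices and metal together without separate reasons. If it has another purpose, add the tumour-field phrase alongside it.

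The cost is one eligibility line in an amendment, sent to the IRB under section 8.5. The downside is that a few patients with metal at the tumour site become ineligible. The rewording does not settle what happens to a scan that proves unreadable after enrolment. A sentence on that in section 7.3 would be a useful companion, but is not needed for this change.

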## 4.0 STUDY PLAN

### 4.1 Schema

### 4.2 Patient Identification and Consent

Patients will be identified at the clinics of the surgical oncologists, orthopedic oncologists, radiation oncologists, and sarcoma multi-disciplinary conference at UNC. Once identified the patients will be recruited and addressed at the clinics of the surgical oncologists, orthopedic oncologists, and/or radiation oncologists at UNC. The recruitment will take place in the privacy of the UNC clinics in private rooms and guided by the subject's treating physicians. Enrollment and informed consent will be facilitated by a study coordinator. Patients will then proceed to treatment as determined by the multidisciplinary tumor board.

### 4.3 Blood Draw for Creatinine

If subjects do not have a serum creatinine value within 30 days prior to a scheduled FDG-PET-MRI scan, they will be required to have a blood draw at UNC Hospitals for creatinine before their FDG-PET-MRI scan visit.

### 4.4 FDG-PET-MRI

All patients will undergo a gadolinium enhanced MRI with simultaneous acquisition of [ $^{18}\text{F}$ ] Fludeoxyglucose Positron Emission Tomography (FDG F18-PET) at the three time points noted.  $^{18}\text{F}$ -FDG is a positron-emitting radiopharmaceutical used for diagnostic purposes. It is a glucose analog that concentrates in cells relying upon glucose as an energy source or in cells whose reliance on glucose increases under pathophysiological conditions. Diabetic patients may need stabilization of blood glucose levels on the day before and on the day of administration of FDG F18.

Injection of gadolinium contrast agent will be performed in the usual manner and images simultaneously obtained with MRI. Patients will have fasted for at least 6 hours before intravenous injection of FDG. To minimize radiation-absorbed dose to the bladder, patients should drink at least an 8 ounce glass of water prior to drug

administration. Whenever possible, patients should take the following precautions for 12 hours after injection: used toilets should be flushed several times after each use, and hands should be washed thoroughly. If blood, urine or feces soil clothing, the clothing should be washed separately.

Each patient will be imaged at three time points as noted. For each visit, patients will be scheduled for PET-MRI imaging at Marsico Hall and will receive imaging-day instructions from the study coordinator. The study coordinator will meet the patient at the imaging facility and escort them to the imaging suite. Women of childbearing potential will undergo repeat urine pregnancy test within 7 days prior to each PET/MRI.

Patients will be paid \$50 each as compensation for their time.

